10.2 Responsibility for Analyses/In-House Blinding

The statistical analyses of the data obtained from this study will be the responsibility of the Clinical Biostatistics department of the Sponsor.

The trial is open-label, ie, participants, investigators, and Sponsor personnel will be aware of participant treatment assignment after each participant is enrolled and treatment is assigned. Allocation to treatment in dose escalation, dose confirmation and coformulation phase will

133

not be randomized. Participants in the efficacy expansion phase will be randomized between Arms F and G.

10.3 Hypotheses/Estimation

Objectives and hypotheses of the study are outlined in Section 4.

10.4 Analysis Endpoints

10.4.1 Efficacy/Immunogenicity/Pharmacokinetics Endpoints

ORR per BICR based on RECIST 1.1 is the primary efficacy endpoint in the efficacy expansion phase. ORR per investigator based on RECIST 1.1 is a secondary endpoint for the dose escalation, dose confirmation, and Arms I and K in the coformulation phase. An objective response is a CR or PR with confirmation. ORR is defined as the portion of participants with CR or PR.

DOR is a secondary endpoint in the efficacy expansion. For participants who demonstrate CR or PR, DOR is defined as the time from first documented evidence of CR or PR until disease progression or death due to any cause, whichever occurs first.

PK endpoints include serum concentrations of MK-1308 and pembrolizumab, as well as derived PK parameters including AUC, C_{min} , and C_{max} . The primary PK parameters for the coformulation phase of MK-1308A would be AUC.

Incidence of ADA is a secondary endpoint.

10.4.2 Safety Endpoints

The primary safety endpoint is number of participants with at least one DLT. In addition, safety and tolerability will be assessed by clinical review of all relevant parameters including AEs, laboratory tests, and vital signs.

A description of safety measures is provided in Section 9.3.

10.5 Analysis Populations

10.5.1 Safety Analysis Populations

The APaT population will be used for the analysis of safety data in this study. The APaT population consists of all participants who received at least 1 dose of study medicine.

DLT-evaluable population: Participants in the APaT population who finished the DLT observation period in the dose escalation phase or DLT observation period in the dose confirmation phase, Arm F in efficacy expansion phase (first 14 participants only), or Arm I without a DLT, or experienced a DLT during the DLT evaluation period will be included in the DLT evaluation. If a participant is replaced due to receiving less than 90% of MK-1308

(or pembrolizumab) in the first cycle, the participant will not be included in the DLTevaluable population.

At least 1 laboratory or vital sign measurement obtained subsequent to at least 1 dose of study treatment is required for inclusion in the analysis of each specific parameter. To assess change from baseline, a baseline measurement is also required.

10.5.2 Pharmacokinetic Analysis Populations

The PP population will be used for the analysis of PK and target engagement data in this study. The PP population consists of the subset of participants who complied with the protocol sufficiently to ensure that their data will be likely to exhibit the effects of treatment, according to the underlying scientific model. Compliance includes such considerations as exposure to treatment, availability of measurements, and the absence of major protocol violations. Any participants or data values excluded from the analyses will be identified, along with the reasons for exclusion, in the CSR. At the end of the study, all participants who were compliant with the study procedures and have available data from at least 1 treatment will be included in the PP analysis dataset.

10.5.3 Efficacy Populations

The APaT population will be the primary analysis population for ORR, PFS and OS. The APaT population consists of all participants who received at least 1 dose of study medicine. The Full Analysis Set (FAS) population will be a supportive analysis population for the ORR analyses. It consists of all participants with a baseline scan that demonstrated measurable disease, and who were administered at least 1 dose of study medicine. Efficacy data occurred during the crossover phase in Arm G will be excluded from the primary efficacy analyses of Arm G or F and may be used in exploratory analyses. For the primary analysis on group comparison between Arm F and Arm G, only the concurrent randomized participants from Arm G participants for the group comparison to support the use of pembrolizumab as part of the combination regimen. Detailed plans of the exploratory analyses will be summarized in the sSAP.

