9.1.8 Treatment Administration

Trial treatment should be administered on the day of treatment allocation/randomization or as close as possible to the date on which the participant is allocated/assigned. Administration of trial medication will be monitored by the investigator and/or trial staff at study visits. The total volume of trial treatment infused will be compared to the total volume prepared to determine compliance with each dose administered.

The instructions for preparing and administering MK-1308, pembrolizumab, and MK-1308A will be provided in the Pharmacy Manual.

MK-1308-001-12 Final Protocol

Study Treatment should begin within 3 days of assignment of randomization number.

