10.1 Statistical Analysis Plan Summary

This section contains a brief summary of the statistical analyses for this trial. Full details are in the Statistical Analysis Plan, Section 10.2 through Section 10.12.

Study Design Overview	Phase 1 / 2 trial of MK-1308 in combination with pembrolizumab in participants with advanced/metastatic solid tumors.	
Analysis Populations	Safety (Primary): All-Participants-as-Treated (APaT), DLT-evaluable population for DLT analysis	
	PK (Secondary): Per-Protocol (PP)	
	Efficacy (Primary in the efficacy expansion phase, and secondary for the other phases): APaT population	

Primary Endpoint(s)	 Safety: Number of participants with at least 1 DLT Number of participants with ≥1 AE Number of participants discontinuing study treatment due to an AE Efficacy (efficacy expansion phase): Objective Response Rate (ORR) defined as the portion of participants with CR or PR as assessed by BICR based on RECIST 1.1, adjusted to follow a maximum of 10 target lesions and a maximum of 5 target lesions per organ)
Secondary Endpoints	ORR as assessed by the investigator based on RECIST 1.1 (dose escalation phase, dose confirmation phase, and Arm I and K in the coformulation phase): DOR as assessed by BICR based on RECIST 1.1 (efficacy expansion phase):
	 The time from first documented evidence of CR or PR until disease progression or death due to any cause, whichever occurs first (for responders only) PK profile and ADA of MK-1308 monotherapy and MK- 1308 in combination with pembrolizumab; PK parameters
	of pembrolizumab in combination with pembrolizumab, FK parameters of pembrolizumab in combination with MK-1308; PK profiles of MK-1308 and pembrolizumab when drugs are sequentially administered, co-administered and coformulated as MK-1308A. • AUC, C _{min} , C _{max}
	Anti-drug antibody levels
Statistical Methods for Efficacy/Immunogenicity/	ORR will be summarized by treatment arm along with a 95% confidence interval.
Pharmacokinetic Analyses	Descriptive summary statistics will be provided for DOR. Time-to-event analysis and Kaplan-Meier estimates may be provided for DOR in addition to the descriptive summary statistics if there are at least 10 responders. PK parameters of study medicines will be summarized by planned visit and time for each dose cohort.

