10.6.1 Statistical Methods for Efficacy Analysis

Objective response rate will be summarized by arm along with a 95% confidence interval. Confidence interval would be calculated using the Clopper–Pearson method. The Miettinen and Nurminen method [Miettinen, O. 1985] will be used for comparison of the ORR between Arm F and Arm G.

Duration of Response will be summarized either using descriptive summary statistics or Kaplan-Meier estimates, depending on the number of responders.

Time to response and best overall response will also be summarized.

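### The randomised Arm F versus Arm G comparison of response rate is restricted to dosed participants; it should use everyone concurrently randomised, as randomised

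*Combined protocol and SAP*

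**What the plan says.** - **Primary set.** Section 10.5.3: "The APaT population will be the primary analysis population for ORR, PFS and OS". The definition follows: "The APaT population consists of all participants who received at least 1 dose of study medicine". The summary in Section 10.1 agrees: "Efficacy (Primary in the efficacy expansion phase, and secondary for the other phases): APaT population".
- **Supportive set.** The Full Analysis Set (Section 10.5.3) is no wider: "It consists of all participants with a baseline scan that demonstrated measurable disease, and who were administered at least 1 dose of study medicine".
- **The randomised contrast.** Section 10.2: "Participants in the efficacy expansion phase will be randomized between Arms F and G". Section 7.3 gives a 1:1 ratio until Arm G reaches 40. Section 10.6.1 says that the Miettinen and Nurminen method "will be used for comparison of the ORR between Arm F and Arm G".
- **The rule specific to that contrast.** Section 10.5.3 begins: "For the primary analysis on group comparison between Arm F and Arm G, only the concurrent randomized participants from Arm G participants". The sentence is incomplete in the copy available and words may have been lost. Its evident purpose is to remove non-concurrent participants, such as those in the Arm F dose-limiting-toxicity run-in.
- **Timing and blinding.** Assignment is known to participants, investigators and sponsor (Section 10.2). Section 9.1.8: "Study Treatment should begin within 3 days of assignment of randomization number".

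**The concern.** A dosed population is sensible for a single-arm response rate, and most of this trial is single-arm. Arms F and G are the exception, and Section 10.5.3 says that their comparison is meant to support including pembrolizumab in the combination. That inference relies on randomisation, which protects the full set of participants assigned to each arm. Here a participant can learn the assignment, leave before the first dose, and be counted in neither defined efficacy population. If such departures relate to the assigned arm or to prognosis, the groups compared are no longer the groups randomised. The readable text also does not say that participants are analysed in the arm to which they were randomised, and it gives no reason for requiring a dose in this comparison.

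**Working it through.** **The plan's own figure.** No stated figure depends on the population choice. The planned total does reproduce from the cohort and arm maxima, which confirms 40 for Arm G: 14 + 14 + 6 (Cohorts 1 to 3) + 4 × 30 + 14 (Arms A to E) + 100 + 40 (F, G) + 20 + 20 (I, K) = 348.

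**Inputs.**
- About 40 versus 40 concurrently randomised (Section 7.3: 1:1 until Arm G has 40).
- Responders 8/40 in F and 2/40 in G. These are assumptions, set at the interim thresholds in Section 5.1.3: 4 of 20 = 20% for F and 1 of 20 = 5% for G.
- Undosed participants: 0 to 4 per arm. This is an assumption, as the documents give no count.

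**Single-arm relation.** If a share d of an arm is undosed and undosed participants do not respond, then ORR(dosed) = ORR(randomised) / (1 − d). At 20%:
- d = 2.5%: 20.5%
- d = 5%: 21.1%
- d = 10%: 22.2%

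**Comparison.** The Miettinen-Nurminen statistic for a difference δ is z(δ) = (pF − pG − δ) / √V. Here V = [p̃F(1 − p̃F)/nF + p̃G(1 − p̃G)/nG] × N/(N − 1), N = nF + nG, and p̃ are the maximum-likelihood rates constrained to differ by δ. The 95% limits are the values of δ at which |z| = 1.96. At δ = 0 both p̃ equal the pooled rate.

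All randomised, 8/40 v 2/40:
- difference = 0.200 − 0.050 = 0.150; pooled rate = 10/80 = 0.125
- V = 0.125 × 0.875 × (1/40 + 1/40) × 80/79 = 0.00554
- z = 0.150/0.0744 = 2.02, p = 0.044

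Dosed only, two undosed in G, 8/40 v 2/38:
- difference = 0.200 − 0.0526 = 0.147; pooled rate = 10/78 = 0.128
- V = 0.128 × 0.872 × (1/40 + 1/38) × 78/77 = 0.00581
- z = 0.147/0.0762 = 1.93, p = 0.053

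| Analysis | F | G | Difference (points) | 95% CI | p |
|---|---|---|---|---|---|
| All randomised, undosed as non-responders | 8/40 | 2/40 | 15.0 | 0.5 to 30.7 | 0.044 |
| Dosed, 2 undosed in G | 8/40 | 2/38 | 14.7 | −0.2 to 30.5 | 0.053 |
| Dosed, 4 undosed in G | 8/40 | 2/36 | 14.4 | −1.0 to 30.3 | 0.065 |
| Dosed, 4 undosed in F | 8/36 | 2/40 | 17.2 | 2.1 to 34.0 | 0.028 |
| Dosed, 4 undosed in each | 8/36 | 2/36 | 16.7 | 0.7 to 33.6 | 0.042 |

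With nobody undosed, every row collapses to the first. Losses in G shrink the difference and losses in F enlarge it.

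**The case against.** The strongest reply is that Section 10.5.3 already has a rule for this contrast, that the sentence is damaged in the available copy, and that the lost words may define the set. That is fair. If the complete sentence names all concurrently randomised participants irrespective of dosing, the point reduces to aligning Section 10.1 with it. The readable words restrict the set by concurrency and do not set aside APaT.

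The second reply is that few participants should go undosed, and most of this stands. The note to Table 3 requires acceptable screening laboratory results before randomisation. Section 9.2.1.1 requires central confirmation of measurable disease before randomisation. Section 9.1.8.1.2 urges first dosing on the day of enrolment, so three days is an outer limit. These steps make exclusions rare, but they do not prevent withdrawal once the assignment is known.

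Three stronger readings are tempting and not supported:
- **That Arm G participants will refuse treatment because the sponsor does not plan to develop MK-1308 monotherapy.** Section 3.2.1.2 states a development plan, which is not evidence of refusal. Arm G also offers crossover after centrally verified progression (Section 5.1.3).
- **That the dosed population favours the combination.** Losses confined to Arm G would make it the more conservative analysis.
- **That unassessed participants are lost as well.** APaT requires no post-baseline scan, so a dosed participant without an assessment already stays in the denominator without a response.

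Finally, the phase is described as gathering preliminary efficacy data, and the readable objectives state no F versus G hypothesis. That limits the stakes. It does not supply a reason to exclude undosed participants.

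**Conclusion.** On the readable text, the plan's only randomised comparison omits randomised but undosed participants, and no defined population restores them. This is a low-cost improvement, not a flaw that threatens the trial. In the illustration, two to four undosed in one arm move the difference by 0.3 to 2.2 points, in a direction that depends on the arm. Such a shift matters only when an interval lies close to zero. A reader might infer that the comparison is materially biased; the documents do not show that, because they give no undosed count and the two analyses coincide if all are dosed. The sizes rest on about 40 per arm, the assumed response rates and the assumed undosed numbers. No conclusion is drawn from the absence of alpha or power for F versus G, since the contents list shows a redaction in that part of the plan.

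**What to change.** In Section 10.5.3, complete the sentence on the F versus G comparison. The primary Miettinen-Nurminen comparison should use all concurrently randomised participants from both arms, analysed as randomised, with undosed participants counted as non-responders. Keep APaT for the by-arm response rates with Clopper-Pearson intervals, and as a sensitivity analysis of the comparison. Report the number undosed, with reasons, by arm. Align the population entry in Section 10.1.

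The cost is wording only, with no new data. Because the opening of Section 10 requires a protocol amendment for changes to methods tied to primary objectives, the text has to go through an amendment with its usual review. As the trial is open-label, the amendment should record which F versus G response data had been seen when the change was made. Reporting both analyses answers any doubt about a late change.

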10.6 Statistical Methods

This section describes the statistical methods that address the primary and secondary objectives.

10.6.1 Statistical Methods for Efficacy Analysis

Objective response rate will be summarized by arm along with a 95% confidence interval. Confidence interval would be calculated using the Clopper–Pearson method. The Miettinen and Nurminen method [Miettinen, O. 1985] will be used for comparison of the ORR between Arm F and Arm G.

Duration of Response will be summarized either using descriptive summary statistics or Kaplan-Meier estimates, depending on the number of responders.

Time to response and best overall response will also be summarized.

10.6.2 Statistical Methods for Safety Analysis

Safety and tolerability will be assessed by clinical review of all relevant parameters including AEs, SAEs, laboratory tests, vital signs, ECG measurements, and physical examinations.

Adverse events will be summarized by counts and frequencies for each arm. Laboratory tests, vital signs, and other safety endpoints will be summarized as appropriate.

Dose-limiting toxicities will be listed and summarized for each arm.

10.6.3 Summaries of Baseline Characteristics, Demographics and Other Analyses

[figure not shown]
10.6.3.1 Demographic and Baseline Characteristics

Demographic variables, baseline characteristics, primary and secondary diagnoses, and prior and concomitant therapies will be summarized.

10.6.3.2 Pharmacokinetic and Pharmacodynamic Modeling Analysis

Pharmacokinetic and pharmacodynamic parameters of MK-1308 monotherapy and MK-1308, administered in combination and in coformulation with pembrolizumab, will be summarized by planned visit and time for each dose cohort/arm.

10.9 Sample Size and Power Calculations

The overall sample size in Cohorts 1 through 3, Arm A, B, C, D and E in this study depends on the observed safety profiles of MK-1308 in combination with pembrolizumab. The maximum sample size is 100 in Arm F and 40 in Arm G. For MK-1308A, the coformulated product, the target sample size is 20 in Arm I, and 20 in Arm K. A target total sample size of 348 participants will be used for study planning purposes.

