 To characterize the PK profiles and incidence of ADA, as appropriate, of pembrolizumab, of MK-1308 as monotherapy, and of MK-1308 when used in combination and in coformulation with pembrolizumab in the dose escalation phase as well as in Arms A, B, C, D, E, F, G, and I. To characterize PK profiles and incidence of ADA of both MK-1308 and pembrolizumab in Chinese participants in Arm K when the study drugs are administered as a coformulated product (MK-1308A). 	 Pharmacokinetic parameters including AUC, C_{min}, C_{max} Anti-drug antibody levels
• To evaluate ORR as assessed by investigator per RECIST 1.1 in the dose escalation phase, the dose confirmation phase, and Arms I and K in the coformulation phase	• Objective response: CR or PR
• To evaluate DOR per RECIST 1.1 as assessed by BICR in the efficacy expansion phase (Arms F and G)	• DOR: The time from first documented evidence of CR or PR until disease progression or death due to any cause, whichever occurs first (for responders only)

Overall Design:

Trial Phase	Phase I / II
Clinical Indication	The treatment of participants with advanced/metastatic solid tumors
Population	Participants ¹ with advanced/metastatic solid tumors
Trial Type	Interventional
Type of design	Uncontrolled, combination, dose escalation, dose confirmation, efficacy expansion
Type of control	No treatment control
Trial Blinding	Unblinded Open-label

Estimated duration of trial	The Sponsor estimates that the trial will require approximately 6 years from the time the first participant signs the informed consent until the last participant's last study-related phone call or visit.
Duration of Participation	Each participant will participate in the study for approximately 3 years from the time the participant provides documented informed consent through the final contact. After a screening phase of 28 days, each participant will receive assigned intervention for approximately 24 months. After the end-of-treatment each participant will be followed for 1 year.
	After the end-of-treatment, each participant will be followed for the occurrence of AEs and spontaneously reported pregnancy. All participants will be followed for overall survival until death, withdrawal of consent, or end of the study.

Number of Participants:

Approximately 348 participants will be enrolled.

A list of abbreviations used in this document can be found in Appendix 1. Study governance considerations are outlined in Appendix 3.

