5.1.1 Dose Escalation Phase for MK-1308 and Pembrolizumab

The projected dose levels are provided in Table 4. A staged dose escalation phase will be instituted whereby the available safety, PK, and pharmacodynamics data from the first 6 participants for each cohort after completion of the DLT period (first 2 cycles) will be evaluated and discussed with the investigators at dose escalation meetings prior to making dose escalation decisions and enrolling additional participants. Initiation of MK-1308 treatment in participants enrolled within each new dose level will be staggered by at least 24 hours for the first 3 participants at that dose level.

Based on the emerging safety and/or efficacy signals, an intermediate dose level may be explored in consultation and agreement with the investigators and Sponsor.

Cohort 1 (n = 6 to 14) will enroll participants with advanced/metastatic **solid tumors**. On Cycle 1, Day 1, participants will receive a single monotherapy dose lead-in with MK-1308 at 25 mg by intravenous route of administration. On Cycle 2, Day 1, and for 3 subsequent cycles on Day 1 (Cycles 3 to 5), these participants will receive MK-1308 at 25 mg in combination with pembrolizumab at 200 mg on a Q3W schedule. For all subsequent cycles (starting with Cycle 6), all participants will receive pembrolizumab monotherapy on a Q3W schedule. A total of 6 participants may be enrolled initially. If \leq 1 participant of the first 6 DLT-evaluable participants has a DLT during the first 2 cycles, Cohort 1 may be expanded to a total of 14 participants in order to obtain additional safety, PK, and pharmacodynamic data; a new cohort will be initiated at the next dose level; and 2 new dose confirmation arms (Arms A and B) at the same dose level will be initiated. If more than 1 DLT occurs in the first 6 DLT-evaluable participants, 6 new participants may be treated at a lower dose level consisting of a single monotherapy lead-in with MK-1308 at an estimated dose of 10 mg, which will be determined by the available safety, PK, and pharmacodynamic data.

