Cohort 2 (n = 6 to 14) will enroll participants with advanced/metastatic solid tumors except NSCLC. Non-small cell lung cancer participants will be excluded from this cohort based on data from the CheckMate-012 study that shows that these participants have unacceptable DLT and discontinuation rates at the equivalent ipilimumab dose of 1 mg per kg [Hellmann, M. D., et al 2016]. On Cycle 1, Day 1, participants will receive a single monotherapy dose lead-in with MK-1308 at 75 mg by intravenous route of administration. On Cycle 2, Day 1, and for 3 subsequent cycles on Day 1 (Cycles 3 to 5), these participants will receive MK-1308 at 75 mg in combination with pembrolizumab at 200 mg on a Q3W schedule. For all subsequent cycles (starting with Cycle 6), all participants will receive pembrolizumab monotherapy on a O3W schedule. A total of 6 participants may be enrolled initially. If <1participant of the first 6 DLT-evaluable participants has a DLT, Cohort 2 may be expanded to a total of 14 participants in order to obtain additional safety, PK, and pharmacodynamic data and 3 new dose confirmation arms (Arms C, D, and E) at the same dose level will be initiated. If more than 1 DLT occurs in the first 6 DLT-evaluable participants, 6 new participants may be treated at a lower dose level or at a different dosing interval which will be determined by the totality of safety, PK, and pharmacodynamic data.

Cohort 3 (n = 6) will enroll participants with advanced/metastatic **solid tumors except NSCLC**. Non-small cell lung cancer participants will be excluded from this cohort. On Cycle 1, Day 1, participants will receive a single monotherapy dose lead-in with MK-1308 at 200 mg by intravenous route of administration. On Cycle 2, Day 1, and for 3 subsequent cycles on Day 1 (Cycles 3 to 5), these participants will receive MK-1308 at 200 mg in combination with pembrolizumab at 200 mg on a Q3W schedule. For all subsequent cycles (starting with Cycle 6), all participants will receive pembrolizumab monotherapy on a Q3W schedule. If more than 1 DLT occurs in the first 6 DLT-evaluable participants, 6 new participants may be treated at a lower dose level or at a different dosing interval which will be determined by the totality of safety, PK, and pharmacodynamic data.

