Arm B (n = 14 to 30) will enroll participants with a diagnosis of advanced/metastatic NSCLC. On Cycle 1, Day 1, participants will receive MK-1308 at 25 mg in combination with pembrolizumab at 200 mg. On all subsequent cycles, pembrolizumab will be given on a Q3W schedule at a dose of 200 mg and MK-1308 will be given on a Q6W schedule at a dose of 25 mg. If \leq 3 of the first 14 participants experience a DLT, after discussion of safety data with the investigators, Arm B will be expanded to 30 participants. If more than 3 DLTs occur in the first 14 DLT-evaluable participants, enrollment of Arm B will not be expanded. Up to 16 participants may be enrolled initially to achieve the desired sample size of 14 DLT-evaluable participants.

Arm C (n = 14 to 30) will enroll participants with a diagnosis of **advanced/metastatic** NSCLC. On Cycle 1, Day 1, participants will receive MK-1308 at 75 mg in combination with pembrolizumab at 200 mg. On all subsequent cycles, pembrolizumab will be given on an every Q3W schedule at a dose of 200 mg and MK-1308 will be given on a Q6W schedule at a dose of 75 mg. If \leq 3 of the first 14 participants experience a DLT, after discussion of safety data with the investigators, Arm C will be expanded to 30 participants. If more than 3 DLTs occur in the first 14 DLT-evaluable participants, enrollment of Arm C will not be expanded. Up to 16 participants may be enrolled initially to achieve the desired sample size of 14 DLT-evaluable participants.

Arm D (n = 14 to 30) will enroll participants with advanced/metastatic SCLC. On Cycle 1, Day 1, participants will receive MK-1308 at 75 mg in combination with pembrolizumab at 200 mg. On all subsequent cycles, pembrolizumab will be given on a Q3W schedule at a dose of 200 mg and MK-1308 will be given on a Q6W schedule at a dose of 75 mg. If \leq 3 of the first 14 participants experience a DLT, after discussion of safety data with the investigators, Arm D will be expanded to 30 participants. If more than 3 DLTs occur in the first 14 DLT-evaluable participants, enrollment of Arm D will not be expanded. Up to 16 participants may be enrolled initially to achieve the desired sample size of 14 DLT-evaluable participants.

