5.2 Number of Participants

This study is expected to enroll approximately 348 participants.

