(MK-1308/pembrolizumab) to be administered every 6 weeks. This formulation and dosing regimen were chosen after data analyses of 215 participants in the dose escalation and dose confirmation phases of the study who were given varying dose levels of MK-1308 (25, 75, and 200 mg every 3 or 6 weeks) and a fixed dose of MK-3475 (200 mg every 3 weeks). Evaluation of the safety, tolerability, PK, pharmacodynamics, and efficacy analysis of this part of the study showed that 25 mg MK-1308 every 6 weeks in combination with MK-3475 every 3 weeks was equally efficacious but safer than the 75 mg and 200 mg MK-1308 dose levels. MK-1308A is being evaluated in this study in advanced solid tumors.

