Treatment Assignment	Participants will be allocated to receive MK-1308 in combination with pembrolizumab (Arms A-F), or MK-1308 monotherapy (Arm G), or the coformulation product MK-1308A (Arm I and K) using an IVRS/IWRS. Treatment assignments in the dose escalation phase, dose confirmation phase and coformulation phase are non- random. Treatment assignments in the efficacy expansion phase will utilize random assignment whenever there is more than 1 treatment arm open.
Statistical Methods for Safety Analyses	Summary statistics will be provided for the safety endpoints as appropriate.
Sample Size and Power	The sample size in Cohorts 1, 2, 3 and Arms A, B, C, D, E of this study depends on the observed DLT profiles of MK-1308 in combination with pembrolizumab. Maximum sample size will be 100 in Arm F and 40 in Arm G. Target sample size will be 20 in Arm I, and 20 in Arm K. A target sample size of 348 participants will be used for study planning purposes.

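### The planning total of 348 rests on 168 early-phase participants, but the same protocol version reports 215 analysed in those phases

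*Combined protocol and SAP*

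**What the plan says.** The total appears four times:

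- Synopsis: "Approximately 348 participants will be enrolled".
- Section 5.2: "This study is expected to enroll approximately 348 participants".
- Section 10.1: "A target sample size of 348 participants will be used for study planning purposes".
- Section 10.9: "A target total sample size of 348 participants will be used for study planning purposes".

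Section 10.9 also sets maxima of 100 for Arm F and 40 for Arm G, and targets of 20 each for Arms I and K. For Cohorts 1-3 and Arms A-E it prints no number and says only that their size follows from the safety results. Their sizes are in Sections 5.1.1 and 5.1.2, for example "Cohort 1 (n = 6 to 14) will enroll participants", "Cohort 3 (n = 6) will enroll participants" and "Arm D (n = 14 to 30) will enroll participants". Cohort 2 has the same range as Cohort 1. Arms A, B and C have the same range as Arm D. Arm E has 6 to 14.

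Section 5.5.3.1, explaining the choice of the MK-1308A regimen, refers to "data analyses of 215 participants in the dose escalation and dose confirmation phases of the study". Section 3.2.1.2 separately gives 179 patients for Arms A, B, C and E.

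**The concern.** The 215 is a report of participants already treated and analysed, not a projection. If the early-phase part of 348 is smaller than that count, the headline size leaves out people whom the same document has already counted. The synopsis and Section 10.9 are where a reader, including an ethics committee or a regulator, looks to learn how many people the study may expose. As printed, 348 and the arm sizes beside it cannot both be taken at face value once the 215 is known. What is at stake is the accuracy of a stated figure. Nothing visible in the plan computes power, an error rate or a stopping boundary from it.

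**Working it through.** **Inputs.** Maxima from Section 5.1.1: Cohort 1, 14; Cohort 2, 14; Cohort 3, 6. Maxima from Section 5.1.2: Arms A, B, C and D, 30 each; Arm E, 14. From Section 10.9: F 100, G 40, I 20, K 20. Reported early-phase count from Section 5.5.3.1: 215.

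**Step 1: reproduce 348.**

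- Dose escalation: 14 + 14 + 6 = 34.
- Dose confirmation: 4 × 30 + 14 = 134.
- Early phases together: 34 + 134 = 168.
- Arms F, G, I and K: 100 + 40 + 20 + 20 = 180.
- Total: 168 + 180 = 348, an exact match.

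Two alternatives fail. Early-phase minima (6 + 6 + 6 + 4 × 14 + 6 = 80) give 260. Cohort 3 at 14 instead of 6 gives 356. The 168 is therefore an inference from the sum, but a well-supported one.

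**Step 2: compare with the reported count.** 215 − 168 = 47, and 47/168 = 28.0%.

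**Step 3: is 215 a misprint?** Section 5.5.3.1 also gives eight common adverse-event percentages from the November 2018 database lock of the same two phases: 24.9, 24.4, 23.5, 22.5, 19.2, 17.4, 16.4 and 16. Assuming they share one denominator, and reading the last as 16.0, the only denominator from 20 to 259 that reproduces all eight is 213. That is close to 215 and far from 168.

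**Step 4: consequence for the total.**

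- Places left within 348: 348 − 215 = 133, which is 133/180 = 73.9% of the stated sizes of F, G, I and K.
- Total on stated sizes: 215 + 180 = 395, and 395 − 348 = 47, or 47/348 = 13.5%.
- Illustrative low case, with F and G ending at 20 each after their efficacy looks and I and K full: 215 + 20 + 20 + 20 + 20 = 295.

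**Step 5: what could account for the 47.**

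- Reallocating unused places among confirmation arms (Section 5.1.2) leaves that phase's total at 134, so it explains none of it.
- PD-L1 top-ups (Section 5.1.2) could add at most 5 × 10 = 50, assuming ten beyond the maximum in every arm: 168 + 50 = 218.
- Replacements (Section 6.5), six new participants at a lower dose or another interval (Section 5.1.1), and intermediate dose levels (Sections 5.1.1 and 5.1.2, Table 4 footnote) could add more. They could also combine with the top-ups.

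None of these enters the sum in Step 1.

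**Step 6: the 179.** Stated maxima for Arms A, B, C and E sum to 3 × 30 + 14 = 104. Taken as labelled, 215 − 179 = 36 remain for Cohorts 1-3 plus Arm D. The stated range for those four groups is 6 + 6 + 6 + 14 = 32 to 14 + 14 + 6 + 30 = 64, so 36 fits.

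**The case against.** The best defence is that 348 was never a cap. Two of the four statements say approximately, and the other two call it a planning target. Section 10.9 ties early-phase size to emerging safety data. Arms F and G are maxima with efficacy looks that can end enrollment, and Arms I and K are described in Section 5.1.4 as up to 20. The final count could therefore be 348 or lower. Much of Section 10.9 may also be blacked out, so an allowance stated there would not be seen.

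The part about attainability stands: 215 does not make 348 impossible. The rest does not remove the mismatch. Uncertainty about early-phase size is a reason for a provisional figure before enrollment, but not for keeping 168 once 215 have been analysed. A gap of 13.5% is more than approximately would normally cover. The exact sum also leaves no room for a hidden allowance unless some arm was planned below its printed size.

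Three stronger readings are tempting, and the documents do not support them:

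- **That participants were enrolled outside the protocol.** The routes in Step 5 may authorise the extra participants.
- **That the total was updated when Arms I and K were added while the early-phase part was overlooked.** No earlier total is visible, so this history is a guess.
- **That the 179 is wrong, for instance that it is really the whole confirmation phase.** It is well above 104, and if Cohorts 1-3 were full (34) only 2 places would be left for Arm D, below its minimum of 14. But nothing shows that the cohorts were full, and the remainder of 36 lies within the stated range.

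**Conclusion.** The point holds as an inconsistency in a stated figure. The visible construction of 348 contains 168 early-phase participants, and the same version reports 215, a difference of 47. Either Arms F, G, I and K together stay at or below 133, or the total exceeds 348. At the sizes printed for those arms it comes to about 395.

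This rests on two assumptions: that the exact match in Step 1 shows how 348 was built, and that the reported 215 is correct, which the adverse-event percentages support. The 395 is neither a forecast nor an absolute ceiling. Futility stops in F and G would lower it. The biopsy-related additions that Section 5.1.3 leaves to the sponsor are not in it and could raise it. The consequence is confined to planning and transparency, since no visible power calculation or decision rule depends on 348.

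**What to change.** In the synopsis and Sections 5.2, 10.1 and 10.9, replace 348 with actual enrollment in Cohorts 1-3 and Arms A-E (215 as reported, to be confirmed) plus the stated sizes for F, G, I and K. On present figures that is about 395. Label it a planning maximum, subject to the futility stops in F and G. State whether PD-L1 top-ups, replacements, added dose groups and biopsy additions are counted.

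Giving the actual number per completed cohort and arm in Sections 5.1.1 and 5.1.2 would make the total checkable. While doing so, check the 179 in Section 3.2.1.2 against actual per-arm enrollment.

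The cost is wording and a check of enrollment records. No participant, arm or decision rule changes.
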